**Supporting Refugee and Immigrant Youth's Mental Health: Examining Effectiveness and Implementation of a
School-Based Intervention**

NCT05208359

02/14/2025

STRONG will be implemented in six public schools during 2021-2022 academic year and six public schools during the 2022-2023 academic year. We anticipate three elementary schools and three high schools each year. Within CPS, school leadership has requested interventions specifically designed for refugee and immigrant students due to school population and need. In each school, one group of approximately five students will be implemented. Schools will be randomly assigned to either provide the STRONG program immediately (immediate treatment) or after three months (delayed treatment). Randomization will include balancing of elementary and high schools so that the number of elementary and high schools randomized to immediate vs. delayed treatment will be equivalent. School mental health staff (e.g., district-employed social workers or community clinicians who provide services in schools) will co-facilitate groups in schools, meeting once a week. School-based clinicians are typically expected to deliver one to two small group interventions as part of their job duties. District partners have committed to supporting clinicians in delivering STRONG as part of this expectation. The research team, comprised of 10 undergraduate students and four graduate students, will collect data at baseline and then at three- and six-months post baseline. Undergraduate and graduate student pairs will meet with students and parents at schools allowing for support and mentorship of undergraduate research assistants along with clinical expertise from graduate students enrolled in the Clinical Psychology PhD program at Loyola University Chicago.

Eligibility Criteria

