Students will be identified by trained STRONG clinicians consistent with standard school procedures, which include teacher and other school staff referral, parent nomination, and clinician identification from other support services. Eligibility criteria include (1) newcomer status (students who have migrated to a new country) and (2) difficulties in functioning or coping as assessed by school staff (teacher, school-based clinician). Referral reasons may include general difficulties, academic performance, peer relationships, family relationships, physical problems, behavioral concerns, and/or appearance of affect, among others. The eligibility criteria are intentionally designed to be broad (i.e., not a strict clinical cutoff) with the purpose of being more inclusive, understanding that cultural and environmental differences may produce different behavioral and emotional outcomes than what typical clinical assessments capture (Alegria et. al, 2008). In addition, researchers call for mental health treatment for refugee and immigrant children that can address trauma, acculturation, isolation, and resettlement, to better address needs (Ellis et. al, 2020). Due to the diversity in experiences, this can also impact the presenting concerns of children during the resettlement process. (Ellis et. al, 2020). Thus, it is important to have a broader inclusion criterion to best fit the needs of this group. This way children that may not be presenting with solely PTSD symptoms, including anxiety, depression, and stress management problems can also benefit from a mental health intervention that highlights their strengths. STRONG allows for this flexibility needed in addressing presenting concerns among this diverse population.

Intervention

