Immediate Treatment						
Group formation	Consent; Randomization ; Baseline/Pre-Treatment Assessment	STRONG Group	Post-Treatment Assessment	Wait Period (No Treatment)	Repeated Post-Treatment Assessment	Data entry & scoring; Preparation for analyses
Delayed Treatment						
Group formation	Consent; Randomization ; Baseline Assessment	Waitlist (No Treatment)	Repeated Baseline Assessment	STRONG Group	Post-Treatment Assessment	
YEAR 3: FALL		WINTER		SPRING		SUMMER
Finish Quantitative Analyses; Code Qualitative Data		Finish Coding Qualitative Data and Conduct Thematic Analysis; Begin preparation for publication		Share findings with partners; Plan future implementation/dissemination; Submit findings for publication; Prepare R01 grant application		

Student Mental Health. Parents, teachers, and students will complete the Strengths and Difficulties Questionnaire (SDQ), a 25-item measure that assesses mental health functioning (Goodman, 1997). It includes a Total Difficulties score and four problem subscales: hyperactivity/inattention scale (e.g., "Restless, overactive, cannot stay still for long"); the emotional symptoms scale (e.g., "Often unhappy, down-hearted or tearful"); the conduct problems scale (e.g., "Generally obedient, usually does what adults request"); the peer problems scale (e.g., "Generally liked by other children"). It also has a prosocial scale (e.g., "Considerate of other people's feelings"). Teachers will complete the SDQ based on their observations of students within their classrooms. Parents will complete the SDQ based on their observations of their child at home. Students will self-report on their mental health. Respondents rate statements on a 3-point scale from *Not true* to *Certainly true*. The SDQ is available in a number of languages including Arabic, Spanish, and Urdu.

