Aim 1. To test the hypotheses that students who participate in STRONG will show improvements in self-reported, parent-reported, and teacher-reported mental health (emotional symptoms, conduct problems, hyperactivity/inattention, and peer problems) as compared to the waitlist control group, repeated measures Analyses of Variance (ANOVA) will be conducted (***Aim 1, Hypothesis 1***). Repeated measures ANOVAs will be conducted on the primary mental health variables (total difficulties, emotional symptoms, conduct problems, hyperactivity/inattention, and peer problems) from baseline to post-treatment to test for a significant Time X Group interaction. Power analyses conducted with GPower (Faul et al., 2006) indicate that a sample size of N=54 is required to detect a Time X Group interaction with a medium effect using two time-points and N=44 utilizing all three repeated measures, suggesting adequate power.

Aim 2. To test the hypotheses that students who participate in STRONG will show improvements in self-reported resilience, coping efficacy, school connectedness and parent-reported coping (***Aim 2, Hypothesis 1***), repeated measures ANOVAs will be conducted on resilience, coping, and school connection from baseline to post-treatment to test for a significant Time X Group interaction. To test the hypothesis that these changes will be related to student mental health improvement/maintenance over time (***Aim 2, Hypothesis 2***), hierarchical linear modeling (HLM) will be utilized. HLM analyses (repeated measures nested within individuals) will allow for an examination of how changes over time on intervention targets (resilience, coping, and school connection) predict student mental health trajectories across all three time-points for the immediate treatment group. This approach is ideal for nested data and capitalizes on all existing time points.

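### Aim 1 makes five SDQ scores primary for three informants, with no testing order, multiplicity adjustment or Aim-level success rule

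*Combined protocol and SAP*

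**What the plan says.** Analytic Strategy, Aim 1, names two outcome sets. The hypothesis concerns "improvements in self-reported, parent-reported, and teacher-reported mental health (emotional symptoms, conduct problems, hyperactivity/inattention, and peer problems", which is four domains by three informants. The analysis sentence then applies repeated measures ANOVA to the "primary mental health variables (total difficulties, emotional symptoms, conduct problems, hyperactivity/inattention, and peer problems", which adds Total Difficulties. The Measures section (Student Mental Health) has all three informants complete the SDQ and says of it: "It includes a Total Difficulties score and four problem subscales".

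Each analysis looks for a significant Time X Group interaction from baseline to post-treatment. The power statement covers one such test: "a sample size of N=54 is required to detect a Time X Group interaction with a medium effect" with two time-points, and N=44 with three. It states no alpha, power or correlation between repeated measures.

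The general paragraph of the Analytic Strategy covers intent to treat, imputation, covariates, outliers and transformations. It says nothing on order of testing, adjustment or what counts as success.

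On design, the opening section says: "Schools will be randomly assigned to either provide the STRONG program immediately", with delayed treatment as the alternative, and "In each school, one group of approximately five students will be implemented".

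**The concern.** With five primary scores and three informants, results can easily be mixed: a teacher-rated score may improve while the parent and student versions do not. The plan does not say how such a pattern would be read.

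A strict reading requires every informant to agree. A loose reading accepts any one significant result. The two carry very different false-positive risks, and the choice could be made after the results are seen. What is at stake is whether a statement that the program improved mental health has a known error rate.

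**Working it through.** **Count (inferred; the plan states none).** 5 scores x 3 informants = 15 tests. 4 domains x 3 informants = 12.

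**The plan's own figures.** For a Time X Group interaction, lambda = f^2 x N x m / (1 - rho), with df1 = m - 1 and df2 = (N - 2)(m - 1). Medium is taken as f = 0.25 (assumed).
- rho 0.50, alpha 0.05, 95% power, m = 2: lambda = 0.0625 x 54 x 2 / 0.50 = 13.5, power 0.950.
- The same inputs with m = 3: lambda = 0.0625 x 44 x 3 / 0.50 = 16.5, power 0.956.
- So 54 and 44 are reproduced. They are also reproduced at alpha 0.05 with 80% power and rho 0.18, and at alpha 0.05/3 with 80% power and rho 0.40. The stated sizes therefore do not show which alpha was planned.

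**False-improvement rate if any one result counts.** The check used 400,000 multivariate normal draws under the null: 12 subscale statistics, plus three totals each taken as the sum of its four subscales (assumed). Each test is two-sided at 0.05, so a single test gives a false improvement 2.5% of the time. The correlations are assumptions.

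| r within / between informants | any of 15 | any of 12 |
|---|---|---|
| 0 / 0 | 0.284 | 0.262 |
| 0.3 / 0.1 | 0.236 | 0.230 |
| 0.5 / 0.3 | 0.189 | 0.187 |
| 0.8 / 0.6 | 0.120 | 0.119 |

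**Strict readings, same draws.** At least one improved score from every informant: 0.001-0.012. All three totals improved: at most 0.005.

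**Three totals only.** Unadjusted, either direction: 0.109-0.143. With Holm: 0.039-0.049 either direction, and 0.020-0.025 for false improvement.

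**Does Holm hold its level here?** Only if each test respects the randomized unit. Simulating 12 schools x 5 students on change scores, with between-informant correlation 0 to 0.6, the either-direction Holm error is:

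| assumed ICC | student-level t-test | school-mean t-test (10 df) |
|---|---|---|
| 0.02 | 0.054-0.062 | 0.044-0.050 |
| 0.05 | 0.072-0.084 | 0.044-0.050 |
| 0.10 | 0.103-0.124 | 0.044-0.050 |

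**Power at Holm's first step.** 0.05/3 = 0.0167; m = 2, f = 0.25, rho 0.18 to 0.50 (the range that reproduces 54/44 at alpha 0.05 with 80-95% power).
- N = 60, ignoring clustering: lambda = 0.0625 x 60 x 2 / (1 - rho) = 9.15 to 15.0. Power goes from 0.85-0.97 to 0.71-0.92.
- 12 school means, ICC 0.05: design effect 1 + (5 - 1) x 0.05 = 1.2, so lambda = 7.62 to 12.5 on 1 and 10 df. Power goes from 0.70-0.89 to 0.49-0.73.
- Self-report is collected only from age 11. The plan says "We anticipate three elementary schools and three high schools each year", so there are six high schools over two years. If only those contribute (N = 6 x 5 = 30), lambda = 3.81 to 6.25 on 1 and 4 df. Power goes from 0.32-0.48 to 0.15-0.24.

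**The case against.** The strongest reply is that Aim 1 speaks of hypotheses in the plural and fixes the test, the contrast and the interval. On that reading each score and informant supports its own claim, and the familywise rate matters only if a global claim is made, which the document does not announce. This is fair, and it rules out saying that the plan intends any one result to suffice. It does not close the gap: all the tests sit under one numbered hypothesis, no alpha is given, and nothing bars a global claim.

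A reader might also infer a rate of 1 - 0.975^15 = 32% for false improvement, or 1 - 0.95^15 = 54% in either direction. Both need 15 independent tests. With each total formed from its own subscales that cannot occur; the largest simulated value for false improvement is 28%.

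A reader might take the four-versus-five mismatch as a serious contradiction. It is a drafting inconsistency: a total summarises the domains, and once scores correlate the choice of 12 or 15 hardly changes the error (0.187 against 0.189 at 0.5/0.3).

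Finally, Total Difficulties with Holm is one valid choice among several, and it demotes the very domains that Hypothesis 1 names. That objection stands, so an alternative is offered below.

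**Conclusion.** The gap is real and should be closed. The plan has 12 or 15 primary tests and no order, adjustment or Aim-level rule. If one significant result were taken to support Aim 1, the chance of at least one false improvement would be about 12-28%, against 2.5% for a single test; under the strict readings it would be about 1% or less. These figures assume two-sided alpha 0.05, tests that keep their level, totals formed as sums, and within/between-informant correlations from 0.8/0.6 down to 0/0.

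A reader might go further and infer that N=54 is wrong, or that it proves an unadjusted 0.05 was planned. The document supports neither: the figure is arithmetically sound for one test, and several combinations of alpha, power and correlation reproduce it.

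**What to change.** State in Aim 1:
- SDQ Total Difficulties, baseline to three months, is the primary score, and Hypothesis 1 is reworded to match.
- It is tested for student, parent and teacher report with Holm at two-sided 5%. Improvement is claimed only for informants whose adjusted test is significant.
- Aim 1 is reported informant by informant with no global claim; otherwise the Aim-level rule is written down.
- Each test accounts for randomization by school, for example through school means, or a mixed model with a school effect and small-sample degrees of freedom.
- The four subscales are secondary, with estimates and confidence intervals.

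Holm or gatekeeping over the four named domains is an acceptable alternative that keeps Hypothesis 1 as worded. Holm over 12 tests starts at 0.05/12 = 0.0042, with power 0.81 at N = 60 and rho 0.50, ignoring clustering.

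**Timing.** The groups are scheduled for 2021-2023, Table 3 places the end of the quantitative analyses in Year 3, and the document is dated 02/14/2025. The data have probably been seen, though this is not confirmed. Label the choice post hoc unless it is confirmed that no outcome data had been examined.

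**Cost.** Wording and a little analysis, with no new data collection. The subscales lose primary status, and a total may dilute a domain-specific effect; Eligibility Criteria shows interest in "children that may not be presenting with solely PTSD symptoms, including anxiety, depression, and stress management problems". Power falls as shown in the working, and the self-report test could be nearly uninformative if only the high schools contribute. The number of students aged 8-10 is not given, so that case is a bound.

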graduation celebration. Between sessions four and eight, students meet individually with the clinician to discuss their journey to the U.S. This may include positive and difficult experiences, including potential traumatic experience. The clinician guides students to recognize strengths that helped them get through their journey rather than focusing on a single event with repeated retelling. The journey narrative is flexible to allow students to discuss multiple traumatic experiences, while also highlighting strengths and assets. It is recommended that the clinician screen for significant PTSD symptoms in individual sessions to consider if additional referrals will be necessary after STRONG. Clinicians also have individual sessions with caregivers and teachers to provide psychoeducation on the children's participation in the STRONG program. This allows for caregivers and teachers to support the student's progress in multiple settings (Hoover et al., 2019).

Participants

An estimated 60 students will participate in STRONG (five students per group across six public schools over two years). Student age range will be 8-18, though each STRONG group will be comprised of students within one grade level of each other. Clinicians, school personnel (teachers, administrators), and parents will be invited to complete measures and participate in focus groups (clinicians) or interviews (teachers, administrators). Teachers who have students participating in STRONG and/or assisted with referrals/identification of students will be recruited to participate in interviews. Teacher participants will be identified in collaboration with school partners/administrators. For example, English Language Learner (ELL) teachers have been key partners in referrals/identification of students in our preliminary feasibility pilot.

Procedure

Clinicians will identify eligible students and reach out to parents/caregivers consistent with standard school procedures. Clinicians will offer a group or individual information meeting to share more about STRONG and will ask parent permission to share contact information with the research team. With permission, the research team will meet with parents as part of the informational meeting or at a later date to provide additional information about the research protocol and obtain informed consent and assent.

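### The power paragraph calls the target a medium effect without defining it; the most natural settings behind N=54 and N=44 imply about a 1 SD difference in change, so adequacy for a 0.5 SD difference is not shown

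*Combined protocol and SAP*

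**What the plan says.** The power statement is one sentence in the combined protocol and SAP (Analytic Strategy, Aim 1). It gives the two-wave requirement as "sample size of N=54 is required to detect a Time X Group interaction with a medium effect using two time-points". The three-wave figure and the conclusion drawn from both follow as "N=44 utilizing all three repeated measures, suggesting adequate power". The software is G*Power. The test is the interaction in a repeated measures ANOVA, run "from baseline to post-treatment to test for a significant Time X Group interaction".

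The Participants section gives the planned size: "An estimated 60 students will participate in STRONG", from five students per group, six schools a year and two years (5 × 6 × 2 = 60). The opening design paragraph randomises whole schools, balanced so that "the number of elementary and high schools randomized to immediate vs. delayed treatment will be equivalent". That is about 30 students and six schools per arm.

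The sentence gives no numerical effect size or definition of it, and no alpha, target power, correlation between repeated measures, allowance for loss or allowance for schools.

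**The concern.** The word medium carries the whole claim. Many readers will take it as a between-arm difference of about 0.5 SD. In G*Power's repeated measures module, f is a different quantity: the f of 0.25 that it labels medium is, for a two-arm, two-wave interaction, a full SD of extra improvement over waitlist. If that value was used, the trial is well powered for a large benefit and roughly a coin toss for a moderate one. A reader who trusts the adequacy statement could then take a null result as evidence against STRONG.

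The calculation also assumes independent students with complete data, whereas the design allocates about 12 schools of about five students each. Any school effect or loss eats into a margin of only six students.

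**Working it through.** **Inputs from the plan.** N=54 (two waves), N=44 (three waves), 60 students planned, two arms at about 1:1, about 12 schools of five.

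**Assumptions.** Alpha 0.05, sphericity, equal SD across waves, and the correlation ρ and target power as shown. None of these is in the plan.

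**1. Reproduce the plan's figures.** For the within-between interaction with two groups and m waves, λ = N·m·f²/(1−ρ), with m−1 and (N−2)(m−1) degrees of freedom. Take f=0.25 and ρ=0.5:
- m=2, N=54: λ = 54 × 2 × 0.0625 / 0.5 = 13.5 on 1 and 52 df; power 0.950.
- m=3, N=44: λ = 44 × 3 × 0.0625 / 0.5 = 16.5 on 2 and 84 df; power 0.956.

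These are the smallest even totals that reach 0.95; two students fewer give 0.942 and 0.946. At the same f and ρ, power 0.80 would need only 34 and 28.

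**2. Translate f into SD units.** Let d be the between-arm difference in change, in outcome SDs. With two arms and two waves, each of the four cells departs from additivity by ±d/4, so f = d/4 and f=0.25 is d = 1.0. The change-score test agrees: λ = N·d²/[4 × 2(1−ρ)] = N·d²/[8(1−ρ)], which is what N × 2 × (d/4)²/(1−ρ) gives. The translation does not depend on alpha, power or ρ. For three waves with between-arm differences (0, d, d) or (0, d, 0), f = d/√18, so f=0.25 is d = 1.06. For linear divergence it is 1.22.

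**3. Is that the only match?** No. These settings also return exactly 54 and 44:
- f=0.125 (0.5 SD with two waves), ρ=0.80, power 0.80. Check at m=2: λ = 54 × 2 × 0.015625 / 0.2 = 8.44; power 0.813.
- f=0.175 (0.7 SD), ρ=0.60, power 0.80.
- f=0.20 (0.8 SD), ρ=0.48, power 0.80.

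**4. What 60 students can detect with two waves.** For d = 0.5, λ = 60 × 2 × 0.015625/(1−ρ) = 1.875/(1−ρ). The last two columns divide λ by a design effect of 1 + 4 × 0.05 = 1.2 (school ICC of change 0.05, an assumption) and use 12 − 2 = 10 error df.

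| ρ | Power for 0.5 SD, independent students | Difference detectable at 80% power | Power for 0.5 SD, ICC 0.05 and 10 df | Detectable at 80%, ICC 0.05 and 10 df |
|---|---|---|---|---|
| 0.5 | 0.48 | 0.74 SD | 0.36 | 0.88 SD |
| 0.6 | 0.57 | 0.66 SD | 0.43 | 0.79 SD |
| 0.7 | 0.69 | 0.57 SD | 0.54 | 0.68 SD |
| 0.8 | 0.85 | 0.47 SD | 0.71 | 0.56 SD |

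At ρ=0.5, 80% power for 0.5 SD would take 128 independent students.

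**5. The margin of 60 over 54.** Loss: 6/60 = 10%. Clustering: 60/(1 + 4·ICC) = 54 gives ICC = (60/54 − 1)/4 = 0.028.

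**6. School-level degrees of freedom alone.** With ICC 0 but 10 error df, 60 students give 0.936 against a target of 0.95 (f=0.25, ρ=0.5). In the three settings of step 3 they give 0.79, 0.78 and 0.78 against 0.80. So in all four settings the planned size falls slightly short of its implied target before any ICC or loss.

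**The case against.** The strongest reply is that nothing in the sentence is miscalculated. If medium means f=0.25, the Ns are right and power at 60 is 0.97. If it means 0.5 SD with ρ=0.80 and target power 0.80, the Ns are again right and power at 60 is 0.85. The plan never says 0.5 SD, so testing it against that benchmark imports a convention. The figure of 48% depends on ρ=0.5, which is inferred. The ICC and the rate of loss are also assumptions, and the Analytic Strategy does promise intent-to-treat analysis and says imputation will be considered.

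Most of this stands. A reader might infer that the Ns can arise only from a 1 SD effect, or that the claim of adequate power is false. The documents support neither inference, because they do not fix f, power or ρ and several combinations fit.

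The reply does not rescue the claim as written. The favourable reading needs both an f of 0.125 to be called medium and a three-month correlation of 0.80, and the plan states neither. Considering imputation does not put an allowance for loss into the sample size. Randomisation by school is in the plan, and the stated Ns can be reproduced with no allowance for it.

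**Conclusion.** The point holds as a gap in what the plan demonstrates, not as an arithmetic error. The target effect is undefined. Under the settings that most naturally give 54 and 44, it is a 1.0 SD difference in change (about 1.06 SD for three waves), and power for 0.5 SD with 60 students is about 48%. Across ρ from 0.5 to 0.8 that power is 0.48 to 0.85 for independent, fully observed students. Adequacy for a 0.5 SD effect is therefore not shown.

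The margin over 54 is too thin to absorb the design: an ICC near 0.03 or a 10% loss removes it. The Measures section adds one certain source of smaller numbers, since students aged 8–10 give no self-report; seven such students would take the self-report analysis to 53.

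The 48% should not be read as the trial's actual power, nor 0.74 SD as the sponsor's design effect, because both rest on an inferred ρ of 0.5. The conclusions assume alpha 0.05, sphericity, equal arms and, where used, the stated ICC. The paragraph should be corrected because readers will rely on it when interpreting a null result, but the matter is not serious enough to block the plan.

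**What to change.** Rewrite the power paragraph under Aim 1 to:
- state the f, alpha, target power and correlation actually used, and which definition of f applies;
- translate f into a between-arm difference in change, in SDs and in SDQ points (the documents give no SDQ SD, so the sponsor must supply one with its source);
- replace the claim of adequacy for a medium effect with the difference detectable at 80% power, for 60 students and for the number expected after loss, separately for each informant;
- show this over a range of correlations (before clustering and loss, about 0.74 SD at 0.5, 0.57 at 0.7 and 0.47 at 0.8);
- include a design effect and error degrees of freedom for about 12 schools, with the ICC range labelled as an assumption.

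This is rewording plus a short recalculation. It needs no extra students. The cost is that the stated power becomes less favourable.
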